4.4 Dose Adjustments based on Genotype

Genotype-guided dose recommendations will be made according to peer-reviewed, evidence-based clinical guidelines from the NIH-funded Clinical Pharmacogenetics Implementation Consortium (CPIC) for 5-FU and capecitabine and the Dutch Pharmacogenetics Working Group (DPWG) for irinotecan (refer to Tables 2 and 3).^{3,12}

Table 2. Genotype-guided dosing recommendations

Drug(s)	Gene	Genotype	Gene Activity Score*	Phenotype	Clinical Implication	Dose Recommendation
5-FU, capecitabine	DYPD	See Table 3 below	2	Normal Metabolizer	Patient is predicted to have a normal risk of toxicity when treated with 5-FU or capecitabine.	Initiate 5-FU or capecitabine at the standard dose.
			1.5	Intermediate Metabolizer	Patient is predicted to have an increased risk of severe toxicity when treated with 5-FU or capecitabine.	Reduce starting dose by 50% followed by dose titration based on toxicity. 5-FU Bolus: if standard dose is 400 mg/m ² , consider 200 mg /m ² 5-FU CIV: If standard dose is 2400 mg/m ² , consider 1200 mg/m ² Capecitabine: If standard dose is 1000-1250 mg/m ² , consider 500-625 mg/m ²

		1	Intermediate Metabolizer	Patient is predicted to have an increased risk of severe toxicity when treated with 5-FU or capecitabine.	
Reduce starting dose by 50% followed by dose titration based on toxicity.
 
5-FU Bolus: if standard dose is 400 mg/m², consider 200 mg /m²
 
5-FU CIV: If standard dose is 2400 mg/m², consider 1200 mg/m²
 
Capecitabine: If standard dose is 1000-1250 mg/m², consider 500-625 mg/m²
	
		0.5	Poor Metabolizer	Patient is predicted to have an increased risk of severe toxicity when treated with 5-FU or capecitabine.	
Avoid use of 5-FU or capecitabine-based regimens. If alternative agents not considered a suitable option, 5-FU should be administered at a strongly reduced dose (i.e. <25% of normal starting dose) with early therapeutic drug monitoring.
	
		0	Poor metabolizer	Patient is predicted to have an increased risk of severe toxicity when treated with 5-FU or capecitabine.	
Avoid use of 5-FU or capecitabine-based regimens.
	
Irinotecan, Liposomal irinotecan	UGT1A1	*1/*1	N/A	Normal Metabolizer	Patient is predicted to have a normal risk of toxicity when treated with irinotecan.	Initiate irinotecan at the standard dose.

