7.5 Data collection at each chemotherapy infusion (time 0 to 6 cycles)

The following information will be assessed at each chemotherapy visit by study personnel or extracted from the medical record with each chemotherapy treatment during the first six cycles if performed as part of usual care and available in the medical record.

- Routine physical examination: height (cm), weight (kg), calculated body mass index (BMI)
- Vital signs: heart rate, blood pressure
- Hematology: hemoglobin, hematocrit, white blood cell count, ANC, neutrophils, eosinophils, basophils, lymphocytes, monocytes, platelets prior to treatment
- Clinical chemistry: sodium, potassium, calcium, glucose, creatinine, BUN, AST, ALT, alkaline phosphatase, total bilirubin, albumin
- Creatinine clearance (using Cockcroft-Gault formula)
- Concomitant medications (including start date, dose, unit, frequency, route of administration and indication)
- Chemotherapy course: dates of treatment, dose of each treatment for first 6 cycles
- Adverse events: date of reported treatment-related symptoms, date of emergency department (ED) visits and/or hospitalizations (if applicable), clinical course and symptom duration, ED/hospitalization medical billing information. Severe TRAEs are defined as those requiring treatment in the hospital, ED, or Oncology Evaluation Center (OEC).
- Serial questionnaires assessing patient reported outcomes (PROs) for symptoms associated with adverse events will be prospectively collected by the study team at the time of each treatment for the first 6 cycles (see data collection tool in Appendix 14.6)

The following information will be extracted from the medical records and/or tumor registry at the 6-month (\pm 2 months) follow-up period if performed as part of usual care and recorded in the medical record.

- Overall patient survival (duration of patient survival from time of treatment initiation)
- Progression free survival (time from treatment initiation until disease progression or worsening)
- Information regarding tumor response from computed tomography (CT) scans will also be collected as available. This is expected to be classified by the treating oncologist as complete response (CR), partial response (PR), stable disease (SD), or progressive

disease (PD) per response evaluation criteria in solid tumors (RECIST) guideline version 1.1.

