8 STATISTICAL PLAN

8.1 Sample size

For the implementation aims, the sample size is based on average GI oncology clinical volume and anticipated number of patients that are eligible for testing. We anticipated testing 500-800 patients during the course of the study at the three Penn Medicine sites. No hypothesis testing will be performed.

For the effectiveness aims, we hypothesize that the chemotherapy-related severe TRAEs will decrease from 60% in the variant carriers receiving full dose chemotherapy in the historical control group enrolled into the PMBB to 30% in variant carriers receiving genotype guided chemotherapy.¹⁸ The following table presents the power for different sample sizes per group and different expected proportions experiencing severe TRAEs in the PGx group, based on two-sided Fisher's exact test at the alpha level of 0.05 (Table 5). Based on the frequencies of *DPYD* and/or *UGT1A1* in the population (~10%), testing 500 patients in each group will result in ~50 patients with actionable genotypes.

Table 5. Power estimate for the reduction in Severe TRAEs with PGx testing

Toxicity rate	39% in PGx	35% in PGx	30% in PGx
N in each group with actionable variants			
18	17.8%	24.8%	35.6%
36	32.3%	45.8%	63.6%
48			80%
54	49.4%	66.3%	83.9%
70		80%	
72	67.4%	82.9%	
97	80%		

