Analysis methods	27	
1. Primary outcome: We will report the number and proportion of tests returned prior to the first dose of chemotherapy in the prospective testing arm only as this outcome was not relevant for the historical control group. The proportions were compared among clinical sites using a chi-square test. The test turn-around time was reported as median (interquartile range) and compared using the Wilcoxon rank-sum test.
 
2. Secondary outcomes:
 
 a. Fidelity- proportion of dose modifications made in agreement with the genotype guided dosing recommendations at the first dose was reported, no hypothesis testing was performed. b. Penetrance- proportion of tests orders divided by the number of patients eligible for testing based on pharmacy records indicating the number of fluoropyrimidine prescriptions during the enrollment time frame, no hypothesis testing was performed. c. Treatment-related adverse events (TRAЕ): proportion of patients experiencing a severe treatment related adverse event defined as those requiring hospitalization, visit to the emergency department, or visit to the oncology evaluation center (OEC). The proportion of patients with severe TRAEs in the prospective cohort were compared between the DPYD variant carriers vs DPYD wild-type patients. The proportion of patients with TRAEs were compared between the prospective and historical control groups among DPYD variant carriers. The proportion of patients with TRAEs in the prospective cohort were compared between the UGT1A1 poor metabolizers vs UGT1A1 normal and intermediate metabolizers. The

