		
proportion of patients with TRAEs were compared between the prospective and historical control groups among UGT1A1 poor metabolizers. Chi-square tests were used for all comparisons. Factors contributing to having a TRAE were evaluated using a multivariable logistic regression model adjusting for age, sex, race, tumor type, ECOG score, presence of metastases, intent of treatment, DPYD phenotype, and UGT1A1 phenotype using a stepwise approach.
 
 d. Relative dose intensity for fluoropyrimidines and irinotecan, defined as cumulative dose administered divided by the anticipated cumulative dose over six cycles reported as mg/m² was compared between variant carriers and wild-type patients (or PM vs. IM/NM for irinotecan) in the prospective cohort using t-tests. Relative dose intensity for fluoropyrimidines and irinotecan, was compared between the prospective and historical control groups in variant carriers (or PM for irinotecan) using t-tests. e. Patient reported outcomes (PROs) during the first six cycles of chemotherapy were compared in the prospective cohort between DPYD variant carriers and wild-type patients using chi-square tests in the subset that completed PROs. f. Patient knowledge and attitudes towards PGx testing were evaluated using chi-square and t-tests as appropriate.
Missing data	28	
 a. Prospective completion of chemotherapy related toxicity per the National Cancer Institute-Common Terminology Criteria for Adverse Events (NCI-CTCAE) was not feasible due to a lack of a consistent research coordinator throughout the study. In addition, the completion rate for the PROs was very low therefore we could not assign a grade to the adverse event. b. Revised definition severe toxicities from \geq Grade 3 toxicities to treatment related adverse events requiring treatment in the hospital, emergency department, or oncology evaluation center.

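### The SAP compares the prospective and historical cohorts for severe TRAEs only among DPYD carriers and UGT1A1 poor metabolizers, with no negative control in patients non-actionable on both genes

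*Combined protocol and SAP*

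**What the plan says.** SAP item 27.2c lists four severe-TRAE comparisons. Two lie within the prospective cohort; for DPYD the text is "The proportion of patients with severe TRAEs in the prospective cohort were compared between the DPYD variant carriers vs DPYD wild-type patients", and UGT1A1 poor metabolizers are likewise set against normal and intermediate metabolizers. The other two compare cohorts: "The proportion of patients with TRAEs were compared between the prospective and historical control groups among DPYD variant carriers", and the "proportion of patients with TRAEs were compared between the prospective and historical control groups among UGT1A1 poor metabolizers". On method: "Chi-square tests were used for all comparisons". A stepwise model follows, described as a "multivariable logistic regression model adjusting for age, sex, race, tumor type, ECOG score, presence of metastases, intent of treatment, DPYD phenotype, and UGT1A1 phenotype"; that list has no term for cohort, calendar period or cohort by genotype. Items 27.2d (relative dose intensity) and 29a (treatment modifications and discontinuations) make their cohort comparisons in the same restricted groups.

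Protocol 8.2.2(1a) is worded differently. It compares the whole PMBB historical group with the whole PGx group by Fisher's exact test, and 8.2.3 repeats this by race.

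For DPYD normal metabolizers Table 2 (protocol 4.4) advises "Initiate 5-FU or capecitabine at the standard dose", and it gives standard-dose advice for UGT1A1 normal and intermediate metabolizers too. Protocol 4.1 describes the historical group as having had no clinical genotyping. On numbers, protocol 8.1 says "testing 500 patients in each group will result in ~50 patients with actionable genotypes".

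**The concern.** The protocol intends to judge effectiveness by comparing severe TRAEs with a historical cohort. Since protocol version 6.0, a severe TRAE is one treated in hospital, the emergency department or the Oncology Evaluation Center. That is a measure of acute-care use, and it can move with calendar period, local care patterns and the way visits are found. Prospective recruitment ran from March 2021 to December 2022. The documents state neither the historical calendar period nor how historical events were found.

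A difference between cohorts among carriers therefore mixes the effect of genotype-guided dosing with anything else that differs between the cohorts. Adjusting for patient covariates cannot separate the two when cohort and period coincide. Patients non-actionable on both genes are a natural check: genotype advice leaves them at standard dosing, so a cohort difference among them points to something other than that advice. The SAP does not look there. Its comparison of carriers with wild-type patients inside the prospective cohort is free of period bias, but it does not estimate the effect of testing and cannot correct the historical contrast.

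**Working it through.** **Inputs.** From protocol 8.1: 60% historical and 30% PGx severe-TRAE rates in carriers, two-sided alpha 0.05, 500 tested and about 50 carriers of either gene per group. Hence 500 − 50 = 450 patients per group are non-actionable on both genes. Assumptions, because the documents give no figure: the size of any cohort shift; a non-carrier event rate of 20-40% (the protocol background cites up to 30% for fluoropyrimidines and 20-35% for irinotecan); and 20-25 carriers per gene per group.

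**1. The plan's own figure.** Full enumeration of the two-sided Fisher test for 60% vs 30% gives 80.0% power at 48 per group and 83.9% at 54. Both match Table 5, so the planned power is not in dispute.

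**2. A pure cohort shift under the SAP's test.** Exact rejection probability of the uncorrected chi-square test, historical rate 60%, prospective rate 60% minus the shift, no PGx effect:

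| Shift (points) | 50 per group | 25 per group | 20 per group |
|---|---|---|---|
| 0 | 5.2% | 6.0% | 4.8% |
| 10 | 18.4% | 13.1% | 8.7% |
| 20 | 54.3% | 33.6% | 22.2% |

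The 50 in protocol 8.1 pools DPYD and UGT1A1, while item 27.2c tests each gene separately. The smaller columns may therefore be nearer to the tests as planned.

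**3. The opposite direction.** Suppose the true effect is 60% to 30% and the prospective rate is raised by 10 points for reasons unrelated to PGx. The test then compares 60% with 40%, and power at 50 per group falls from 87.6% to 54.3%.

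**4. What the non-carrier contrast can show.** With 450 per group and a rate p, the 95% CI half-width is 1.96 × √(2p(1−p)/450): 5.2 points at p = 20% and 6.2 at p = 35%. Power to detect a 10-point fall is about 99% and 91% respectively.

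**5. Cost of subtracting it, on the risk-difference scale.**
- Carrier variance: 0.6×0.4/50 + 0.3×0.7/50 = 0.0090, SE 0.0949.
- Added variance, 2p(1−p)/450: 0.00071 at p = 20%, 0.00107 at p = 40%.
- Variance ratio: 0.00971/0.0090 = 1.08 to 0.01007/0.0090 = 1.12.
- Power, Φ(0.30/SE − 1.96): 88.5% for the carrier difference alone, 85-86% after subtraction. Simulation of the subtracted estimate gives 84-85%.
- Under common shifts of 0, 10 and 15 points with no PGx effect, its simulated rejection rate stays at 5.4-5.7%.

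**6. Why the scale matters.** A common shift in percentage points is not a common shift in odds. Take a 15-point fall in everyone, with carriers going from 60% to 45% and non-carriers from 20% to 5%. The odds ratios are (0.45/0.55)/(0.60/0.40) = 0.55 and (0.05/0.95)/(0.20/0.80) = 0.21. Their ratio is about 2.6, which would look like harm from testing. A logistic cohort-by-genotype interaction then rejects falsely about 52% of the time (about 15% for a 10-point fall). Its power for 60% vs 30% with no shift is about 80-82%.

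**The case against.** Five arguments weigh against the point.

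- *The combined plan does have a contrast that could reveal drift.* This stands. On the figures in 8.1, about 90% of the patients in the whole-cohort comparison of 8.2.2(1a) are non-carriers. A 30-point effect in the other 10% moves the total by only 3 points, whereas a 10-point drift would be detected with about 91-98% power at 500 per group (non-carrier rates 20-40%). A reader might infer that nothing planned could expose a shift, and that would be wrong. But the contrast pools both kinds of patient and cannot apportion a difference, and the SAP does not carry it forward.
- *Fuller staff follow-up of prospective patients is not shown.* This also stands. Protocol 7.5 says data "will be assessed at each chemotherapy visit by study personnel or extracted from the medical record"; the Schedule of Activities says severe TRAEs are abstracted from records; there are no study-specific visits; and prospective grading was abandoned for want of a consistent coordinator. It is tempting to read ascertainment bias into the design, but the documents leave its existence and direction open.
- *All shift sizes are hypothetical.* True. The figures show sensitivity and are not evidence of bias.
- *A negative control brings its own assumption.* True. It removes only a shift common to both genotype groups on the chosen scale. That is weaker than assuming no shift at all, which the carrier contrast needs.
- *Effectiveness is secondary in a feasibility study.* True; this limits the weight of the point. The primary outcome is unaffected.

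**Conclusion.** The point holds for the SAP. Its cohort comparisons of severe TRAEs are confined to DPYD carriers and UGT1A1 poor metabolizers, are unadjusted, and have no companion estimate in patients whose dosing advice the test leaves at standard. If a cohort-wide shift exists, a carrier test at nominal 5% rejects about 18% of the time for 10 points and about 54% for 20 points at 50 per group, or about 9-13% and 22-34% at 20-25 per gene per group. These figures assume a 60% historical rate, no PGx effect and equal groups. The 450 non-carriers per group are implied by protocol 8.1; the number achieved is not stated. The documents do not support the stronger conclusions that a shift occurred, that the carrier result is biased, or that a logistic interaction should be the sole basis for a PGx claim.

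**What to change.** Keep the carrier and poor-metabolizer contrasts in item 27.2c and add:

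1. The prospective-minus-historical risk difference for severe TRAEs, with 95% CI, among patients non-actionable on both DPYD and UGT1A1, presented as a negative control. DPYD wild-type alone is not enough, because such a patient may be a UGT1A1 poor metabolizer.
2. As a supporting analysis, the carrier risk difference minus the non-carrier risk difference, with the additive scale stated in advance. Any claimed PGx effect should be interpreted in its light.
3. A statement reconciling item 27.2c with protocol 8.2.2(1a), together with the historical calendar period, how historical events were found, and the number of genotyped historical non-carriers.

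The SAP places the analyses in May-June 2024, so anything added afterwards should be labelled post hoc.

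The statistical cost is the 8-12% extra variance shown above and the assumption of a common shift on the risk-difference scale. The practical cost is severe-TRAE data for historical non-carriers under the current definition. Protocol 8.2.2(1a) already calls for these data, but the documents do not say how many were abstracted. If few are available, the non-carrier rates with their intervals would still help readers judge the carrier result.

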7.3 Implementation Metrics (0-14 days)

The following information if available will be collected to determine the feasibility of PGx test implementation and agreement to the PGx guided dosing recommendations:

- Dates of sample collection, return of PGx test within PennChart, and timing of first dose of chemotherapy
- Intended and prescribed doses of chemotherapy
- Reasons for not adhering to the PGx guided recommendations
- The proportion of tests ordered compared to the number eligible for testing.

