8.2 Overview of statistical methods

Descriptive statistics (mean, SD, median, interquartile range, range, counts, and percentage) will be used to describe and compare (t-test or rank sum test for continuous variables and Fisher's exact test for categorical variables) baseline characteristics between the historical control group and PGx arms.

8.2.1 Implementation Endpoint(s):

- We will report the number and proportion of tests returned prior to the first dose of chemotherapy.
- We will report the proportion of dose modifications made in agreement with genotype-guided dosing recommendations at the first dose.
- The proportion of tests ordered compared to the number eligible for testing.

8.2.2 Secondary Endpoint(s):

1. Clinical endpoints

- a. The proportion of patients experiencing severe TRAEs will be compared in the PMBB historical control group vs. the PGx group using Fisher's exact test.

Subgroup analyses will be performed by tumor type.

- b. The relative dose intensity (RDI) will be calculated for 5-FU, capecitabine or irinotecan as the cumulative administered dose divided by the anticipated cumulative dose over the first 6 cycles. RDI will be compared in the PMBB historical control group vs. the PGx group using linear regression adjusted for sex, race, BMI, tumor type, cancer stage, line of therapy and ECOG performance status.

Subgroup analyses will be performed by tumor type.

2. Patient reported outcomes

Patient reported outcomes as assessed on a Likert scale will be reported as means (SD) and compared between the PMBB historical control group vs. the PGx group using linear regression adjusting for age, sex, race, tumor type, cancer stage, BMI, line of therapy, and ECOG performance status.

3. Patient attitudes toward PGx testing

Patient knowledge and attitudes towards PGx testing will be assessed on a Likert scale will be reported as means (SD). We will compare results by sex, race, tumor type, and insurance status by using linear regression. (See survey in Appendix 14.7)

8.2.3 Tertiary Endpoint(s):

1. Clinical endpoints in minority populations

The proportion of patients experiencing severe TRAEs will be compared in the PMBB historical control group vs. the PGx group using Fisher's exact tests, stratified by race.

2. Minor allele frequencies will be reported by ancestry for the DPYD and UGT1A1 genes.
3. Medical services utilization and costs

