We will obtain data from Data Analytics Center (DAC) on service utilization and costs. These will include: number of physician visits; number of emergency department visits; number of hospitalizations; length of hospital stay; number of emergency department and hospital admissions associated with drug-related adverse events; DPYD and UGT1A1

genetic testing costs; physician visit cost; emergency department visit costs; hospitalization costs; inpatient and physician-administered medication costs; and total costs. Care Everywhere will be utilized to obtain information if patients received care outside Penn Medicine. Additionally, medical records will be requested for admissions that occur outside of Penn Medicine.

We will compare utilization and costs incurred by the PMBB usual care group with utilization and costs incurred by the PGx group using Poisson regression methods (for number of visits), and linear regression methods with appropriate transformations (e.g., log-transform, winsorization) to account for skewness in utilization and cost distributions.

4. Survival Analysis

Overall survival and progression free survival at approximately six months will be compared between the PMBB historical control group vs. the PGx group by use of Kaplan-Meier estimators and log-rank tests. Cox proportional regression analysis will be performed to adjust for clinical covariates including age, sex, race, tumor type, cancer stage, BMI, and ECOG performance status.

5. Pre-treatment uracil and fluoropyrimidine associated toxicity

First, we will examine the range of pre-treatment uracil concentrations with the association of severe toxicity to determine if there is a cut-off whereby toxicity occurs. Previous studies have proposed uracil $> 16\text{g/ml}$ as highly predictive for severe toxicity, but we will validate this cut-off in our patient population.¹⁵ We will also examine whether the pre-treatment uracil levels vary in *DPYD* variant carriers. Second, we use logistic regression models to determine the risk of severe toxicity including a binary factor for uracil concentration (above and below cut-off), with adjustment for age, sex and treatment regimen.

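### Chemotherapy regimen is controlled in no severe-TRAE comparison, so a different regimen mix in the prospective and historical cohorts could be read as a PGx effect

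*Combined protocol and SAP*

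**What the plan says.** **Severe TRAEs, SAP Section 6, item 27.2c.** Four comparisons are specified: DPYD carriers against wild-type, and UGT1A1 poor metabolizers against the rest, both within the prospective cohort; then prospective against historical patients, once among DPYD carriers and once among UGT1A1 poor metabolizers. The test is stated in one line: "Chi-square tests were used for all comparisons". Separately, a stepwise model is described: "Factors contributing to having a TRAE were evaluated using a multivariable logistic regression model adjusting for age, sex, race, tumor type, ECOG score". The list goes on to metastatic status, treatment intent and the two gene phenotypes. It contains neither a regimen term nor a cohort term.

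**Severe TRAEs, protocol 8.2.2 and 8.2.3.** The cohort comparison is a Fisher's exact test, with subgroups by tumor type and a version stratified by race. Regimen does not appear.

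**Where regimen does appear.** The uracil toxicity model in protocol 8.2.3 is fitted "with adjustment for age, sex and treatment regimen". Protocol 8.3 also lists chemotherapy among the clinical data for the microbiome adjustment.

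**Other outcomes.** The protocol plans relative dose intensity (RDI) by "linear regression adjusted for sex, race, BMI, tumor type, cancer stage, line of therapy and ECOG performance status", a similar regression for patient-reported outcomes (PROs), and a Cox model with "clinical covariates including age, sex, race, tumor type, cancer stage, BMI, and ECOG performance status". None names regimen. The SAP does not carry these models forward. Under the SAP, RDI "was compared between the prospective and historical control groups in variant carriers (or PM for irinotecan) using t-tests", PROs are compared by chi-square within the prospective cohort, and one-year survival is only reported.

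**Treatments admitted.** Protocol 4.1 admits patients starting 5-FU or capecitabine, irinotecan, or both. Protocol 2.2 describes partner drugs that vary between irinotecan, oxaliplatin and targeted agents.

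**The concern.** The outcome is toxicity of the drugs given, and the drugs given vary from patient to patient. A model meant to identify what contributes to a TRAE leaves out which drugs were received, while another toxicity model in the same protocol includes them.

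Two results are at stake. The first is the prospective-versus-historical contrast. The controls are earlier biobank patients, and no matching or restriction by regimen is described. If regimens with more toxicity were commoner in one cohort, the unadjusted test would credit or charge the difference to PGx testing. The baseline lists (protocol 7.4, SAP item 25) cover previous treatment but not the current regimen, so an imbalance might not even be displayed.

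The second is UGT1A1. Protocol 14.4.1 describes its role through irinotecan's active metabolite, and Table 2 ties its recommendations to irinotecan formulations only. SAP item 18 removes only patients tested after chemotherapy or given no qualifying drug, so patients on a fluoropyrimidine without irinotecan stay in the UGT1A1 comparisons and in the UGT1A1 model term.

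**Working it through.** **1. The plan's own figure.** Protocol 8.1 and Table 5 give 80% power for 60% versus 30% with 48 carriers per group, by a two-sided Fisher's exact test at 0.05. Enumerating all pairs of binomial outcomes gives 80.05%. The other 80% entries come out at 80.95% (70 per group, 35%) and 80.6% (97 per group, 39%). All 14 filled cells reproduce to within 1 point. Nothing in Table 5 is wrong on this account; it supplies the planned effect, 60 − 30 = 30 points.

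**2. Formula for the bias.** Take a lower-risk and a higher-risk regimen with TRAE risks r1 and r2. Let m be the share of a cohort on the higher-risk one. With no PGx effect, the cohort's TRAE rate is r1 + (r2 − r1) × m. The spurious cohort difference is therefore (difference in risk) × (difference in share):

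- 0.10 × 0.10 = 0.01, or 1 point
- 0.20 × 0.20 = 0.04, or 4 points
- 0.30 × 0.30 = 0.09, or 9 points

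All these inputs are assumed. Neither document gives the regimen mix or the TRAE risk by regimen.

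**3. Effect on the chi-square test.** Assume 48 carriers per group, no PGx effect, shares centred on 50%, and the higher-risk regimen commoner in the historical group. Two illustrative risk pairs are used: 20% and 35% (the ends of the severe-toxicity range quoted for irinotecan in protocol 2.2) and 30% and 60% (the two rates in protocol 8.1). Neither pair is offered in the documents as a gap between regimens.

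Example with 30% and 60% and a 30-point imbalance: the shares are 65% and 35%. Historical: 0.30 + 0.30 × 0.65 = 0.495. Prospective: 0.30 + 0.30 × 0.35 = 0.405. Difference: 0.090.

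| Imbalance in share | 20%/35%: spurious difference | 20%/35%: false-positive rate | 30%/60%: spurious difference | 30%/60%: false-positive rate |
|---|---|---|---|---|
| 0 points | 0 | 5.2% | 0 | 5.1% |
| 10 points | 1.5 | 5.5% | 3.0 | 6.1% |
| 20 points | 3.0 | 6.4% | 6.0 | 9.2% |
| 30 points | 4.5 | 8.0% | 9.0 | 14.6% |
| 40 points | 6.0 | 10.3% | 12.0 | 22.2% |

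If the imbalance ran the other way, the same number of points would hide a benefit. The 48 is the protocol's figure for actionable carriers of either gene. The SAP splits the contrast by gene, so its groups would be smaller; the bias in points does not depend on group size.

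**4. UGT1A1.** Let d be the TRAE difference by UGT1A1 phenotype among irinotecan-treated patients, and s the share of patients given irinotecan, taken as equal across phenotypes. If the phenotype does not affect toxicity without irinotecan, the pooled difference also depends only on treated patients and equals s × d. It falls short of d whenever s is below 1. The documents do not give s.

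**The case against.** **The omission alone proves no bias.** With a balanced mix the bias is zero, and no imbalance is documented. This stands: the point is a credible risk, not a demonstrated error.

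**Adding regimen to the logistic model does not touch the cohort contrast.** That contrast is a chi-square test, and the model has no cohort term. This also stands, and it is why the contrast itself needs an adjusted or stratified version. Because selection is stepwise, a listed regimen term could also be dropped.

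**Proxies exist.** Tumor type, metastatic status and treatment intent are in the model, and the protocol plans tumor-type subgroups. They carry part of the information, but one tumor type can receive several regimens, and none of them enters the SAP cohort tests. RDI is scaled to the anticipated dose of each drug, and the Cox list is worded as open-ended, so the argument is weaker for those outcomes than for TRAEs.

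**Stronger readings that do not hold.** A reader might infer that regimen is confounded with genotype. Genotype is germline, patients whose genotype is known are excluded (protocol 5.2), and race is already in the model, so genotype should not drive the regimen chosen before the result. After the result, regimen can be part of the recommendation (protocol Table 2), and adjusting for it could remove part of the effect under study. A reader might also take the pre-result regimen to be on file under protocol 7.3. That section lists "Intended and prescribed doses of chemotherapy", collected if available. These are doses, and nothing says they were fixed before the result came back. Finally, the absence of age from the RDI list and of line of therapy from the Cox list is a matter of preference, not a defect shown here.

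**Conclusion.** The concern holds as a limited one. Regimen is controlled in no TRAE group comparison in either document, and the protocol's uracil model shows that its authors regarded regimen as relevant to toxicity. A difference in mix between the cohorts could therefore be read as a PGx effect. The likely size is modest: about 1 to 9 points if mix and risk each differ by 10 to 30 points, against 30 planned. In the wider illustrations it reaches 12 points at a 40-point imbalance. It is zero if the mix is balanced, and all the inputs are assumptions. At the upper end the false-positive rate is well above 5%, so the mix should be shown rather than presumed equal. The UGT1A1 effect may also be diluted in proportion to the share of patients not given irinotecan. No stated power or sample-size figure changes.

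**What to change.** 1. **Model in item 27.2c.** Add regimen (fluoropyrimidine alone, plus oxaliplatin, plus irinotecan, plus both) as a forced term outside the stepwise selection. Assign a level to any patient given irinotecan without a fluoropyrimidine, since eligibility admits them. Use the regimen intended before the PGx result where the chart records it, and otherwise the first regimen given. Add a sensitivity analysis for switches that followed the result.
2. **Cohort contrast.** Report the regimen mix by cohort and genotype. Beside each chi-square test of carriers, give a version adjusted for or stratified by regimen.
3. **UGT1A1.** Restrict the TRAE analysis to irinotecan-treated patients, defined by the same regimen rule, or add a UGT1A1-by-irinotecan term.
4. **Other models.** If the protocol's RDI, PRO and Cox models are still run, add regimen there too.

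**Cost.** Four regimen levels add 4 − 1 = 3 parameters, plus any extra level or interaction. That is a real burden in small carrier groups, where coarser strata may be needed. The drugs and doses given are collected for prospective patients when charted (protocol 7.5). Historical controls, and any pre-result intention, will need some chart abstraction. SAP item 14 dates the analyses to May–June 2024, so the additions should be labelled as sensitivity analyses.
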